3. OBJECTIVES, ENDPOINTS, AND ESTIMANDS

Table 3 Study objectives, endpoints and estimands

Objectives	Endpoints and estimands
Primary	
To evaluate the reactogenicity and safety of the HSVTI.	
 Percentage of participants reporting each solicited administration site event (redness, pain, and swelling) within 7 days (Day 1-Day 7) post-each dose. Percentage of participants reporting each solicited systemic event (fever, fatigue, headache, myalgia, arthralgia) within 7 days (Day 1-Day 7) post-each dose. Percentage of participants reporting unsolicited AEs within 28 days (Day 1-Day 28) post-each dose. Percentage of participants reporting MAEs from Dose 1 (Day 1) up to 28 days post-Dose 2 (Day 57). Percentage of participants reporting SAEs from Dose 1 (Day 1) up to 28 days post-Dose 2 (Day 57). Percentage of participants reporting newly diagnosed pIMDs from Dose 1 (Day 1) up to 28 days post-Dose 2 (Day 57). Percentage of participants reporting exacerbation of pre-existing pIMDs from Dose 1 (Day 1) up to 28 days post-Dose 2 (Day 57). Percentage of participants reporting any hematological and biochemical laboratory abnormalities at pre-study intervention administration (Day 1), post-Dose 1 (Day 8 and Day 29), and post-Dose 2 (Day 36 and Day 57).
Secondary	
To evaluate the humoral immune response induced by the HSVTI.	
 CCI antibody GMC and seropositivity rate (assessed by ELISA) at pre-study intervention administration (Day 1), 28 days post-Dose 1 (Day 29), and 28 days post-Dose 2 (Day 57).
To evaluate the cellular immune response induced by the HSVTI.	
 Geometric mean of CCI CD4+/CD8+ T-cells frequency expressing at least 2 activation markers (IFN-γ, TNF-α, IL-2, IL-13, IL-17, 4-1BB and/or CD40L) and including at least one cytokine (assessed by CFC) at pre-study intervention administration (Day 1), 28 days post-Dose 1 (Day 29) and 28 days post-Dose 2 (Day 57).
To evaluate the safety of the HSVTI up to the end of follow-up period.	
 Percentage of participants reporting MAEs from Dose 1 (Day 1) up to study end (Day 209). Percentage of participants reporting SAEs from Dose 1 (Day 1) up to study end (Day 209). Percentage of participants reporting newly diagnosed pIMDs from Dose 1 (Day 1) up to study end (Day 209). Percentage of participants reporting pre-existing pIMDs from Dose 1 (Day 1) up to study end (Day 209).

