7.1.1. Contraindications to subsequent study intervention(s) administration

The eligibility for subsequent study intervention administration must be confirmed before administering any additional dose.

Participants who meet any of the criteria listed below should not receive additional doses of study intervention. Such participants should be encouraged to continue other study procedures, at the investigator's discretion (Section 10.3.9.2). All relevant criteria for discontinuation of study intervention administration must be recorded in the eCRF.

- Participants who experience any SAE judged to be related to study intervention or non-study concomitant vaccine/product.
- Participants who develop any new condition which, in the opinion of the investigator, may pose additional risk to the participants if they continue to participate in the study.
- Occurrence of a new pIMD or the exacerbation of an existing pIMD that, in the opinion of the investigator, expose the participant to unacceptable risk from subsequent vaccination. In such cases, the investigator should use his/her clinical judgment prior to administering the next dose of study intervention. Refer to Section 10.3.6.1 for the definition of pIMDs.
- Abnormal hematological and biochemical parameters, unless the laboratory abnormalities are considered temporary or not clinically significant by the investigator.
- Occurrence of an AE assessed as related to the study intervention following the previous dose administration, which may place the participant at unreasonable or significant risk of injury or illness following repeat exposure to study intervention, based on the investigator's judgment.
- Anaphylaxis or other hypersensitivity reactions following the administration of study intervention.
- Any condition that in the judgment of the investigator would make intramuscular injection unsafe.
- Pregnant or lactating.

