9.2. Analysis sets

Table 14 Analysis sets

Analysis set	Description
Screened set	All participants who were screened for eligibility
Enrolled set	All participants who entered the study (who were randomized or received study intervention or underwent a post-screening procedure)
Exposed Set (ES)	All participants who will receive at least 1 dose of the study intervention.
Per Protocol for immunogenicity set (PPS_Immuno)	All eligible participants who will receive all doses as per protocol, will have immunogenicity results post-dose, will comply with dosing/blood draw intervals, without intercurrent conditions that may interfere with immunogenicity and without prohibited concomitant medication/vaccination. The analysis will be done according to the study intervention that participants received at dose 1.
Per Protocol for CMI set (PPS_CMI)	All eligible participants who will receive all doses as per protocol, will have CMI results post-dose, will comply with dosing/blood draw intervals, without intercurrent conditions that may interfere with immunogenicity and without prohibited concomitant medication/vaccination. The analysis will be done according to the study intervention that participants received at dose 1.

CCI

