9.3.3. Primary Endpoints/Estimands Analyses

The analysis of the primary reactogenicity and safety objective will be performed on the ES.

Statistical Analysis Methods

The percentage of participants reporting at least one solicited AE, at least one solicited administration site AE, and at least one solicited systemic AE during the 7-day follow-up period (i.e., Day 1-Day 7 post-each study intervention administration) will be tabulated for each group after each dose and overall.
 
The percentage of participants reporting each individual solicited administration site AE (any grade and Grade 3) and solicited systemic AE (any grade and Grade 3) during the 7-day follow-up period (i.e., Day 1-Day 7 post-each study intervention administration) will be tabulated for each group after each dose and overall.
 
For solicited AEs, percentages will be computed based on the total number of solicited symptoms screens completed.
 
For each group and for each hematology and biochemistry parameter:
 
• The percentage of participants having hematology and biochemistry results below or above the laboratory normal ranges will be tabulated by timepoint.• The summary of grading post-study intervention administration will be tabulated vs. baseline. Grades will be based on the FDA Guidance for Industry “Toxicity Grading Scale for Healthy Adults and Adolescent Volunteers Enrolled in Preventive Vaccine Clinical Trials”; see Section 10.2.2). The laboratory parameters not included on FDA Toxicity Grading Scale will not be graded. 
The percentage of participants with any unsolicited AEs during the 28-day follow-up period (i.e., Day 1-Day 28 post-each study intervention administration) with its exact 95% CI will be tabulated by group and by MedDRA PTs. Similar tabulation will be done for Grade 3 unsolicited AEs, for any causally related unsolicited AEs, for Grade 3 causally related unsolicited AEs and for unsolicited AEs resulting in a medically attended visit. The verbatim reports of unsolicited AEs will be reviewed by a qualified person and the signs and symptoms will be coded according to the MedDRA Dictionary for Adverse Reaction Terminology. Every verbatim term will be matched with the appropriate PT.
 
For unsolicited AEs, percentages will be computed based on the total number of exposed participants. Participants not reporting an AE will be considered as not having experienced any AE.
 
The percentage of participants with any AEs (solicited and unsolicited) resulting in a medically attended visit from Dose 1 up to 28 days post last dose administered (Day 57, or Day 29 if only one dose administered) will also be tabulated by MedDRA SOC and PT by group, after each dose and overall with exact 95% CI.
 
The percentage of participants with at least one report of SAE, with at least one report of causally related SAE, with at least one report of fatal SAE, and with at least one report of causally related fatal SAE classified by the MedDRA SOC and PTs reported from Dose 1 up to 28 days post last dose administered (Day 57, or Day 29 if only one dose administered) will be tabulated by group with exact 95% CI.
 
The percentage of participants with at least one newly diagnosed pIMD and at least one exacerbation of a pre-existing pIMD classified by the MedDRA SOC and PTs and reported from Dose 1 up to 28 days post last dose administered (Day 57, or Day 29 if only one dose administered) will be tabulated by group with exact 95% CI.
 
The percentage of participants using concomitant medication (any medication, any antipyretic, and any antipyretic taken prophylactically, respectively) during the 7-day follow-up period (i.e., Day 1-Day 7 post-each study intervention administration) and during the 28-day follow-up period (i.e., Day 1-Day 28 post-each study intervention administration) will be summarized by group after each dose and overall.

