
9.3.4. Secondary Endpoints/Estimands Analyses

The analysis of the secondary humoral immunogenicity objectives will be performed on the PPS for analysis of immunogenicity (PPS_immuno). The analysis of the secondary CMI objectives will be performed on the PPS for analysis of CMI (PPS_CMI). If more than 10% of participants are eliminated from any of the PPS in any treatment group, a sensitivity analysis will be carried out using the ES. The analysis of the secondary safety objective will be performed on the ES.

Statistical Analysis Methods
The percentage of participants with any AEs (solicited and unsolicited) resulting in a medically attended visit from Dose 1 up to study end (Day 209) will also be tabulated by MedDRA SOC and PT by group, after each dose and overall with exact 95% CI.
The percentage of participants with at least one report of SAE, with at least one report of causally related SAE, with at least one report of fatal SAE, and with at least one report of causally related fatal SAE classified by the MedDRA SOC and PTs reported from Dose 1 up to study end (Day 209) will be tabulated by group with exact 95% CI.
The percentage of participants with at least one newly diagnosed pIMD and at least one exacerbation of a pre-existing pIMD classified by the MedDRA SOC and PTs and reported from Dose 1 up to study end (Day 209) will be tabulated by group with exact 95% CI.
For each group, at each timepoint that blood samples are collected for immune responses and for each assay (unless otherwise specified):

• Seropositivity rates and their 95% CI will be tabulated.• GMCs/GMTs and their 95% CI will be tabulated and represented graphically. CCI [REDACTED]• Mean geometric fold increases and their 95% CI will be tabulated and represented graphically. CCI [REDACTED]• Percentage of participants that had a study intervention response defined as a 4-fold increase in concentration and their CI will be tabulated by group. CCI [REDACTED].• Antibody titer/concentration will be displayed using reverse cumulative curves.• The kinetics of titers will be plotted as a function of time for participants.• The frequency of specific CD4+/CD8+ T-cells will be summarised (mean, SD, minimum, Q1, median, Q3, and maximum) by group, at each timepoint during which blood samples are collected for CMI (descriptive statistics).

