### 1.1. Objectives, Estimands and Endpoints

Objectives	Endpoints and Estimands
Primary	
To evaluate the reactogenicity and safety of the HSVTI.	
 
Percentage of participants reporting each solicited administration site event (redness, pain, and swelling) within 7 days (Day 1-Day 7) post-each dose.
 
Percentage of participants reporting each solicited systemic event (fever, fatigue, headache, myalgia, arthralgia) within 7 days (Day 1-Day 7) post-each dose.
 
Percentage of participants reporting unsolicited AEs within 28 days (Day 1-Day 28) post-each dose.
 
Percentage of participants reporting MAEs from Dose 1 (Day 1) up to 28 days post-Dose 2 (Day 57).
 
Percentage of participants reporting SAEs from Dose 1 (Day 1) up to 28 days post-Dose 2 (Day 57).
 
Percentage of participants reporting newly diagnosed pIMDs from Dose 1 (Day 1) up to 28 days post-Dose 2 (Day 57).
 
Percentage of participants reporting exacerbation of pre-existing pIMDs from Dose 1 (Day 1) up to 28 days post-Dose 2 (Day 57).
 
Percentage of participants reporting any hematological and biochemical laboratory abnormalities at pre-study intervention administration (Day 1), post-Dose 1 (Day 8 and Day 29), and post-Dose 2 (Day 36 and Day 57).
 

Secondary	
To evaluate the humoral immune response induced by the HSVTI.	
 
CC1 antibody GMC and seropositivity rate (assessed by ELISA) at pre-study intervention administration (Day 1), 28 days post-Dose 1 (Day 29), and 28 days post-Dose 2 (Day 57).
 

To evaluate the cellular immune response induced by the HSVTI.	
 
Geometric mean of CC1 CD4+/CD8+ T-cells frequency expressing at least 2 activation markers (IFN-<math>\gamma</math>, TNF-<math>\alpha</math>, IL-2, IL-13, IL-17, 4-1BB and/or CD40L) and including at least one cytokine (assessed by CFC) at pre-study intervention administration (Day 1), 28 days post-Dose 1 (Day 29) and 28 days post-Dose 2 (Day 57).
 

To evaluate the safety of the HSVTI up to the end of follow-up period.	
 
Percentage of participants reporting MAEs from Dose 1 (Day 1) up to study end (Day 209).
 
Percentage of participants reporting SAEs from Dose 1 (Day 1) up to study end (Day 209).
 

Objectives	Endpoints and Estimands

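### For one-dose participants the primary SAE, MAE and pIMD analyses close at Day 29, an exception absent from Table 3 and SAP 1.1, so counting a later event depends on whether Dose 2 followed

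*Protocol*

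**What the plan says.** **Endpoint.** Protocol Section 3, Table 3, lists among the primary endpoints "Percentage of participants reporting SAEs from Dose 1 (Day 1) up to 28 days post-Dose 2 (Day 57") and, in the same form, "Percentage of participants reporting newly diagnosed pIMDs from Dose 1 (Day 1) up to 28 days post-Dose 2 (Day 57"). Exacerbations of pre-existing pIMDs have the same window. SAP 1.1 repeats the list, for example "Percentage of participants reporting MAEs from Dose 1 (Day 1) up to 28 days post-Dose 2 (Day 57"). Neither table mentions participants who receive one dose only. A note under Table 3 sends the reader to Section 9 for the handling of intercurrent events.

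**Primary analysis.** Protocol 9.3.3 analyses MAEs, SAEs and pIMDs "from Dose 1 up to 28 days post last dose administered (Day 57, or Day 29 if only one dose administered"). The analysis set is the Exposed Set, defined in 9.2 as "All participants who will receive at least 1 dose of the study intervention", so a one-dose participant remains in the denominator.

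**Collection and follow-up.** Section 10.3.9.1 has SAEs, MAEs and pIMDs recorded from Day 1 to Day 209, without reference to Dose 2. For participants barred from a further dose, 7.1.1 says: "Such participants should be encouraged to continue other study procedures", at the investigator's discretion.

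**Secondary analysis.** Section 9.3.4 has SAEs and pIMDs "reported from Dose 1 up to study end (Day 209) will be tabulated by group with exact 95% CI", and MAEs over the same period. On the set it says: "The analysis of the secondary safety objective will be performed on the ES". The Day 29 cut does not apply there.

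**The concern.** The endpoint and its analysis have different windows for the same participants. Under 9.3.3 a one-dose participant is watched for half of the time that Table 3 implies, yet counts as a full member of the denominator.

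The window's end is also fixed by something that happens after Dose 1. Most criteria in 7.1.1 for withholding Dose 2 concern safety: a related SAE, a new or worsened pIMD, abnormal laboratory values, a related AE, hypersensitivity. If such an event starts after Day 29 but before Dose 2 would have been given, it closes its own window retrospectively and drops out of the primary table. The primary percentage then partly reflects the dosing decision as well as the event rate.

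At stake is the Day 57 safety readout, which is the primary analysis. For SAEs and pIMDs in groups of 20, 20 and 10, the difference between none and one is likely to be the result that people read.

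**Working it through.** **1. The plan's own days.** Dose 1 on Day 1 plus 28 days is Day 29. Dose 2 on Day 29 plus 28 days is Day 57. Both figures in 9.3.3 reproduce. Table 3 spans 57 − 1 = 56 days. The one-dose rule spans 29 − 1 = 28 days, so (57 − 29)/56 = 50% of the window is outside the primary tables.

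**2. Can the event that stops dosing fall outside the window?** Protocol Table 2 allows Visit 3 at 28 to 33 days after Visit 1, that is Day 29 to Day 34. Section 5.5 allows up to 90 days between doses in special circumstances such as a hold, that is up to Day 91. Take two participants due for Dose 2 on Day 34, each with a first SAE on Day 32:

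| | Participant A | Participant B |
|---|---|---|
| SAE judged | related | not related |
| Dose 2 (7.1.1) | withheld | given on Day 34 |
| Primary window ends (9.3.3) | Day 29 | Day 34 + 28 = Day 62 |
| SAE in the primary table | no | yes |

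Onset is the same day in both. The related SAE is left out and the unrelated one is counted.

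pIMDs have a further route. Section 10.3.6.1 withholds the pIMD label until a definitive diagnosis, and 9.3.3 counts pIMDs reported within the window. If the date of diagnosis governs, symptoms before Day 29 that are diagnosed afterwards are also outside. The readable text does not say which date governs.

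**3. Effect of one omitted participant.** Exact (Clopper-Pearson) 95% intervals, the method in SAP 4.1.1. For x = 0 the upper limit is 1 − 0.025^(1/n). For n = 20 this is 1 − 0.025^(1/20) = 16.8%.

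| Group size | Event counted | Event omitted |
|---|---|---|
| 20 | 1/20 = 5.0% (0.1–24.9%) | 0/20 = 0% (0–16.8%) |
| 10 (placebo) | 1/10 = 10.0% (0.3–44.5%) | 0/10 = 0% (0–30.8%) |

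**4. Illustrative range.** The documents give neither the number of one-dose participants nor event rates, so these inputs are assumptions: m = 1 to 4 one-dose participants in a group of 20, a constant 28-day risk r of 1% to 20% that is the same with or without Dose 2, and complete follow-up.

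- Expected fall in the group percentage: (m/20) × r(1 − r). For m = 1, r = 0.01: 0.05 × 0.0099 = 0.05 percentage points. For m = 4, r = 0.20: 0.20 × 0.16 = 3.2 points.
- Chance that at least one participant's only event is omitted: 1 − (1 − r(1 − r))^m. For the same two cases: 1 − 0.9901 = 1%, and 1 − 0.84^4 = 50%.

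The range is wide because the inputs are unknown. It is not a forecast for this trial.

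**The case against.** **Section 9.3.3 may be a deliberate rule.** Table 3 ties its window to Dose 2, which a one-dose participant never has. The note under Table 3 points to Section 9, and 9.3.3 spells out both cases. A window of 28 days after the last dose also matches the collection of unsolicited AEs. This stands in part: the rule is explicit and could be a legitimate estimand. But Table 3 and SAP 1.1 do not carry it, the readable text gives no reason for it, and it still makes the counting of an event depend on the dosing decision that follows.

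**The event that bars Dose 2 is normally counted.** It usually starts by Day 29, and a participant already counted stays counted whatever follows. This stands for most cases. It is not assured, as step 2 of the working shows.

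**Nothing is lost, and oversight is unaffected.** A reader might infer that these events disappear. They do not. Collection runs to Day 209 and the secondary tables use the same set without the cut. The internal safety review committee reviews all accumulated safety data about monthly (8.2.3), and holding rules 1a–1d apply whatever the timing of the event (8.2.3.1). This stands. The Day 209 backstop is somewhat clearer for SAEs and pIMDs than for MAEs, because the call description in 8.3.6 does not name MAEs, though Table 1 and 10.3.9.1 do.

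**Follow-up after one dose is not guaranteed.** Continuation is encouraged but discretionary. Extending the window for people who left would treat unobserved time as event-free. This stands, and the fix has to report it.

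**A plain Day 57 cut-off would be worse in one case.** If Dose 2 is delayed to Day 91, a fixed Day 57 cut-off excludes every event after Dose 2, whereas the last-dose wording runs to Day 91 + 28 = Day 119. This stands and shapes the fix.

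**Conclusion.** The mismatch is real and confined to the primary tables. For one-dose participants, 9.3.3 covers 28 of the 56 days stated in Table 3 and SAP 1.1, and whether an event after Day 29 is counted depends on a later dosing decision that the event may itself cause. One affected participant moves a group of 20 between 0% and 5.0%, or the placebo group between 0% and 10.0%. How many would be affected is unknown.

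Two stronger readings are tempting. One is that participants stop after one dose often for safety reasons. The 7.1.1 criteria make that plausible, but 7.1 also lists unwillingness and other reasons, and no frequencies are given. The other is that the primary percentages are biased low without qualification. They can be too low only against the Table 3 window to Day 57. Against a declared window of 28 days after the last dose there is no such bias.

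The conclusion rests on the readable text. SAP 4.6 places the main safety analyses in Section 4.2, which is redacted and may repeat or alter the rule. SAP 4.8 declares no change from the protocol. The study is descriptive, so no test or error rate is involved.

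**What to change.** 1. In Protocol 9.3.3 and the matching SAP section, count SAEs, MAEs and pIMDs for every exposed participant up to the later of Day 57 and 28 days after the last dose received, as far as follow-up was observed. This gives Day 57 for one dose, Day 57 for two doses on the planned days, and a later date when Dose 2 is delayed.
2. Report by group how many participants received one dose only, and how many of them were followed to Day 57.
3. Keep the present version, 28 days after the last dose, as a supplementary table.
4. Align Table 3 and SAP 1.1 with this wording.

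The cost is wording in both documents and one extra table. No new data are needed, since collection already runs to Day 209. The remaining limitation is that some Day 30–57 time will be unobserved in one-dose participants who left the study.

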
9.3.4. Secondary Endpoints/Estimands Analyses

The analysis of the secondary humoral immunogenicity objectives will be performed on the PPS for analysis of immunogenicity (PPS_immuno). The analysis of the secondary CMI objectives will be performed on the PPS for analysis of CMI (PPS_CMI). If more than 10% of participants are eliminated from any of the PPS in any treatment group, a sensitivity analysis will be carried out using the ES. The analysis of the secondary safety objective will be performed on the ES.

Statistical Analysis Methods
The percentage of participants with any AEs (solicited and unsolicited) resulting in a medically attended visit from Dose 1 up to study end (Day 209) will also be tabulated by MedDRA SOC and PT by group, after each dose and overall with exact 95% CI.
The percentage of participants with at least one report of SAE, with at least one report of causally related SAE, with at least one report of fatal SAE, and with at least one report of causally related fatal SAE classified by the MedDRA SOC and PTs reported from Dose 1 up to study end (Day 209) will be tabulated by group with exact 95% CI.
The percentage of participants with at least one newly diagnosed pIMD and at least one exacerbation of a pre-existing pIMD classified by the MedDRA SOC and PTs and reported from Dose 1 up to study end (Day 209) will be tabulated by group with exact 95% CI.
For each group, at each timepoint that blood samples are collected for immune responses and for each assay (unless otherwise specified):

• Seropositivity rates and their 95% CI will be tabulated.• GMCs/GMTs and their 95% CI will be tabulated and represented graphically. CCI [REDACTED]• Mean geometric fold increases and their 95% CI will be tabulated and represented graphically. CCI [REDACTED]• Percentage of participants that had a study intervention response defined as a 4-fold increase in concentration and their CI will be tabulated by group. CCI [REDACTED].• Antibody titer/concentration will be displayed using reverse cumulative curves.• The kinetics of titers will be plotted as a function of time for participants.• The frequency of specific CD4+/CD8+ T-cells will be summarised (mean, SD, minimum, Q1, median, Q3, and maximum) by group, at each timepoint during which blood samples are collected for CMI (descriptive statistics).

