8.1.2. Laboratory assays

Table 8 Laboratory assays

Assay Type	System	Component	Method	Laboratory
Screening	Serum	Anti-HSV antibodies	Western Blot	University of Washington Molecular Virology laboratory
Humoral immunity (antibody determination)	Serum	CCI [REDACTED] antibodies	ELISA	GSK* or in a laboratory designated by GSK
Cell-mediated immunity	PBMC	CCI [REDACTED] (CD4+/CD8+) T-cells	CFC	

ELISA: enzyme-linked immunosorbent assay; CCI [REDACTED] HSV: herpes simplex virus;

PBMC: peripheral blood mononuclear cell; CD4+/CD8+: cluster of differentiation 4/8; CFC: cell flow cytometry

* GSK laboratory refers to the Clinical Laboratory Sciences (CLS) in Rixensart, Belgium; Wavre, Belgium.

Please refer to Section 10.2 for a brief description of the assays performed in the study.

The addresses of clinical laboratories used for sample analysis are provided in a separate document accompanying this study protocol.

CCI

Note that tertiary objectives and endpoints/estimands are optional and might be assessed only if needed; therefore, not all related testings might be performed and reported.

CCI

Additional exploratory testing on the disease under study may be performed within the framework of the study if deemed necessary for accurate interpretation of the data or should such assay(s) become available at GSK's laboratory or a laboratory designated by GSK. These assay(s) may not be represented in the objectives/endpoints/estimands of the Protocol and may be described in ancillary study Protocol(s), as needed.

GSK clinical laboratories have established a Quality System supported by procedures. The activities of GSK clinical laboratories are audited regularly for quality assessment by an internal (sponsor-dependent) but laboratory-independent Quality Department.

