10.8. Appendix 8: Abbreviations and glossary of terms

10.8.1. List of abbreviations

AE	Adverse Event
ALT	Alanine aminotransferase
AST	Aspartate aminotransferase
CD4+/CD8+	Cluster of differentiation 4/8
CD40L	Cluster of differentiation 40 ligand
CFC	Cell flow cytometry
CI	Confidence Interval
CIOMS	Council for International Organizations of Medical Sciences
CMI	Cell-mediated immunity
COVID-19	Coronavirus disease 2019
CPL	Clinical Project Lead
CSL	Clinical Sciences Lead
CSR	Clinical Study Report
DNA	Deoxyribonucleic acid
eCRF	electronic Case Report Form
ELISA	Enzyme-linked immunosorbent assay
EoS	End of Study

ES Exposed Set

CCI

FDA Food and Drug Administration, United States of America

FSFV First subject first visit

FSH Follicle-stimulating hormone

GCP Good Clinical Practice

CCI

GMC/GMT Geometric Mean Concentration/ Geometric Mean Titer

GSB Global Safety Board

GSK GlaxoSmithKline Biologicals SA

HIPAA Health Insurance Portability and Accountability Act

HIV Human Immunodeficiency Virus

CCI

HRP Horseradish peroxidase

HRT Hormonal replacement therapy

HSV Herpes Simplex Virus

HSV-TI HSV-targeted immunotherapy

IB Investigator's Brochure

ICF Informed Consent Form

ICH International Council for Harmonization

ICMJE International Committee of Medical Journal Editors

IEC Independent Ethics Committee

IFN- γ Interferon-gamma

IgA/G/M Immunoglobulin A/G/M

IL (IL-2, IL-13, IL-17) Interleukin

IRB	Institutional Review Board
iSRC	Internal Safety Review Committee
LML	Local Medical lead
LSLV	Last Subject Last Visit
MAE	Medically Attended Event
MedDRA	Medical Dictionary for Regulatory Activities
MHC I/II	Major Histocompatibility Complex I/II
CCI	
PBMC	Peripheral blood mononuclear cell
pIMD	Potential immune-mediated disease
PPS	Per Protocol Set
PT	Preferred term
CCI	
QTL	Quality Tolerance Limit
RNA	Ribonucleic acid
SAE	Serious Adverse Event
SAP	Statistical Analysis Plan
SAS	Statistical analysis system
SBIR	Source data Base for Internet Randomization
SD	Standard Deviation
SOC	System Organ Class
SPM	Study Procedures Manual
SRT	Safety Review Team
SUSAR	Suspected Unexpected Serious Adverse Reaction

CCI

TNF- α Tumour necrosis factor-alpha

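### Does protocol 9.3.4 leave out the geometric mean T-cell frequency that is declared as the secondary cellular endpoint?

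*Protocol*

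**What the plan says.** The endpoint is worded the same way in both documents, apart from the redaction mark that hides the antigen. Protocol Table 3 (section 3) has "Geometric mean of CCI CD4+/CD8+ T-cells frequency expressing at least 2 activation markers" and SAP 1.1 has "Geometric mean of CC1 CD4+/CD8+ T-cells frequency expressing at least 2 activation markers". Both add that at least one cytokine must be among the markers, that flow cytometry (CFC) is the assay, and that the timepoints are Day 1, Day 29 and Day 57.

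Protocol 9.3.4 then lists immune-response summaries for each group and timepoint, "for each assay (unless otherwise specified"). The list includes "GMCs/GMTs and their 95% CI will be tabulated and represented graphically. CCI [REDACTED" and "Mean geometric fold increases and their 95% CI will be tabulated and represented graphically. CCI [REDACTED", where the closing marks show that further text is blacked out. The last bullet is the one on cells: "The frequency of specific CD4+/CD8+ T-cells will be summarised (mean, SD, minimum, Q1, median, Q3, and maximum) by group". It carries a closing label saying that these are descriptive statistics.

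Four other places bear on the reading:
- Protocol 9.3 says that it summarises the analyses and that the SAP holds the technical detail.
- Protocol 9.1 and SAP section 2 state that nothing is tested and everything is descriptive.
- SAP 4.1.1 gives a general rule for continuous data (n, mean, SD, median, minimum, maximum).
- SAP 6.2.3.4 defines geometric means for titers and concentrations.

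**The concern.** An endpoint table and an analysis section should name the same statistic. Here the table names a geometric mean, while the visible T-cell bullet lists seven statistics and leaves that one out. Antibody concentrations in the same list get a geometric mean with a 95% confidence interval. The abbreviation list expands the term as "GMC/GMT Geometric Mean Concentration/ Geometric Mean Titer", which does not obviously cover a cell frequency, and a fold increase is not a level. The visible SAP does not settle the matter: its geometric-mean rules (6.2.3.4 and 6.2.4.4) speak of titers and concentrations, and 4.8 records no change to the protocol's analyses.

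If the bullet were the whole plan, the report could give an arithmetic mean of skewed frequencies where the reader expects a geometric mean. The reader would also have no measure of the estimate's precision.

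**Working it through.** The plan gives no figure to reproduce, because there is no hypothesis, power or margin for this endpoint. The check is first a comparison of texts and then a short calculation.

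**Step 1: what is fixed.** Table 3 and SAP 1.1 state the summary measure, the cell population, the assay and the days. Protocol 9.3.4 assigns the analysis to PPS_CMI and by group. What remains is to compute and tabulate the statistic.

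**Step 2: does the T-cell bullet contradict this?** It would if it replaced the geometric mean. Nothing in it says so, and its label as descriptive statistics fits a supplement showing the distribution. Both statements can be followed at once.

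**Step 3: could another bullet already cover it?** The lead-in applies the list to every assay unless specified otherwise, and "Table 8 Laboratory assays" in protocol 8.1.2 sets CFC beside ELISA. The GMC/GMT and fold-increase bullets may therefore extend to T-cells. The abbreviations point towards antibodies, and the text after both bullets is hidden, so this stays open.

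**Step 4: does the visible SAP show an omission?**
- SAP 4.1.1 gives no geometric mean for any continuous variable. Antibody concentrations are continuous too and still get GMCs, so its silence says nothing about T-cells.
- SAP 6.2.4.4 is headed as a serology section, so T-cells would not be expected there.
- The N/A in SAP 4.8 fits either reading, because reporting the endpoint in Table 3 changes nothing in the protocol.
- SAP 4.6 points to section 4.2 for the main safety analyses, so the endpoint analyses lie in the pages between 4.1.2 and 4.6. Those pages are redacted. Text hidden by redaction cannot be counted as missing.

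**Step 5: how far apart are the statistics?** The documents give no SD, so assume log-normal frequencies with SD s on the natural-log scale.

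Arithmetic mean / geometric mean = exp(s²/2):
- s = 0.5: exp(0.125) = 1.13
- s = 1.0: exp(0.5) = 1.65
- s = 1.5: exp(1.125) = 3.08

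The arithmetic mean is therefore no substitute for the geometric mean. In the same model, however, median / geometric mean = exp(μ)/exp(μ) = 1 for every s, where μ is the mean on the log scale. The bullet lists the median with Q1 and Q3, so even the listed set contains an estimate of the declared quantity.

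**Step 6: the confidence interval.** Had one been declared, the factor each way would be exp(t × s/√n). Planned group sizes are 20 (each HSVTI group) and 10 (placebo).

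| | s = 0.5 | s = 1.0 | s = 1.5 |
|---|---|---|---|
| n = 20, t = 2.093 | 1.26 | 1.60 | 2.02 |
| n = 10, t = 2.262 | 1.43 | 2.04 | 2.92 |

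These factors show how imprecise the estimate may be. They do not show a departure from the plan, because neither Table 3 nor SAP 1.1 promises an interval for this endpoint.

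**The case for a change.** The best case for acting is that the mismatch is visible whatever the redacted pages hold. A summary long enough to list seven statistics could have named the declared one. The lead-in's exception for cases specified otherwise could also be taken to mean that the T-cell bullet sets its own, complete list. In a descriptive study the estimate and its precision are the result, and checking the full SAP before the statistician is unblinded at the Day 57 analysis would cost almost nothing.

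The wording point stands: the bullet does not repeat the statistic, and a reader of 9.3.4 alone would not learn of it. The rest falls short of a defect. A short summary bullet does not override an endpoint definition that appears in both documents. The request to check the SAP concedes that the statistic may already be there. A confidence interval would be a useful extra, but it is a preference.

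One practical detail is not visible: how zero frequencies enter a log transform, or negative ones if the medium-only control described in protocol 10.2.1 is subtracted. The visible substitution rule in SAP 6.2.3.3 is for serology, and the missing-data rules in SAP 6.2.2 are redacted. This detail cannot be called absent either, and it does not alter which statistic is declared.

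**Conclusion.** The observation is correct as a matter of wording, and it calls for no change to the plan. The geometric mean is pre-specified by the endpoint itself, the T-cell bullet can be read beside it without conflict, and the text that would settle the detail is redacted. An analyst following the plan would report geometric mean frequencies by group at Days 1, 29 and 57 and show the listed statistics next to them.

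The effect is negligible. No sample size, error rate or visible decision rule depends on the bullet, and no data collection is affected. The gap between arithmetic and geometric mean (1.13 to 3.08) rests on assumed log-SDs and a log-normal shape. It would matter only if the arithmetic mean were reported in place of the endpoint, which nothing in the documents directs.

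This conclusion assumes that Table 3 governs what is reported for the endpoint and that the bullet is supplementary. Were the full SAP to state that the bullet's list replaces the geometric mean, the point would have to be reopened.
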